465 An inspiratory chest CT scan will be performed using a reduced dose protocol that utilizes
466 dose modulation. Dose modulation automatically adjusts x-ray exposure for each patient to
467 achieve a consistent level of image quality. The reference mAs for this scan will be set
468 such that an average sized subject (~75 kg) with a normal build would receive an x-ray
469 exposure (CTDIvol) of 3.0 mGy (corresponding roughly to an effective dose of 1.5mSv).
470 X-ray exposure will automatically be adjusted higher or lower for larger or smaller
471 subjects. The maximum exposure for the dose modulation acquisition will be set at 3.0
472 mSv. The scans will be processed using filtered back projection and (where feasible)
473 iterative reconstruction. An expiratory CT acquisition will be performed using a fixed x-
474 ray tube current of 50 mAs to assess for air trapping.

475 Results of the CT scan will be provided to the subject. Subjects will be asked to consent if
476 they would like their results sent to their primary care physician. If any clinically
477 significant findings are found on the CT scan, they will be automatically sent to the
478 primary care provider.

479
480 If the chest CT scans are done on the same day as the post-bronchodilator spirometry, the
481 scan should be scheduled as soon as possible after albuterol. The time and date of the last
482 bronchodilator medication use prior to the CT scan will be captured. CT scans will be
483 electronically transmitted to the Imaging Core at National Jewish Health by secure FTP
484 site.

485 13. The 30 second sit to stand test will be performed. The purpose is to test leg strength and
486 endurance. Blood pressure and heart rate will be checked prior to performing the test.
487 Contraindications would be patients at high fall risk specifically amputees without
488 prosthesis, individuals who need an assistive device for ambulation, subjects with a short
489 term lower extremity impairment, and patients who have had previous stroke with
490 significant residual deficits in balance or proprioception. The subject will sit in a chair with
491 hands placed on the opposite shoulders and crossed at the wrists, then will rise to a full
492 standing position and then sit back down again, repeating the maneuver as many times as
493 possible within 30 sections. The number of times the subject comes to a full standing
494 position is recorded.

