671 trapping, six minute walk distance (6MWD), and health-related quality of life. Longitudinal
672 analyses will be performed with quantitative imaging phenotypes from the Phase 1, 2, and 3
673 visits. Key predictor variables to be assessed for these outcomes include age, gender, current
674 smoking status (at each visit), pack-years, baseline lung function, baseline CT emphysema and
675 airway measures, respiratory symptoms (e.g., chronic bronchitis, dyspnea), respiratory
676 medications, and co-morbid illnesses (including lung cancer and coronary artery disease).
677 Exacerbation frequency will be assessed as a predictor of primary outcome measures.
678 Transformations of CT and spirometric progression measures from among the Box-Cox family
679 of transformations will be considered to stabilize variance estimates across the ranges of CT
680 measurement values. We will compare the demographic and clinical characteristics of subjects
681 who have follow-up data to those subjects missing due to death and those subjects missing due to

682 loss to follow-up. Longitudinal analysis will be performed including time-dependent covariates
 683 such as change in current smoking status. Time-dependent covariates in these analyses include
 684 change in current smoking status and change in pulmonary medications. Disease progression and
 685 mortality will be simultaneously assessed to limit potential bias introduced by differential
 686 survival. This analytical approach considers the joint distribution of the vector of repeated
 687 measures (i.e., longitudinal progression of PFT abnormalities and CT measures) simultaneously
 688 with time to event (i.e., mortality) using the method developed by Hogan and Laird(10).
 689 The power to detect differences in 10-year changes between subtypes of COPDGen subjects
 690 was assessed for FEV₁, PERC15, adjusted lung density, and % gas trapping. These calculations
 691 used the mean and standard deviation (SD) with estimated changes in FEV₁(11), PERC15(12),
 692 adjusted lung density, and % gas trapping based on the 5-year follow-up visits. We assumed a
 693 significance level of 0.05 and equal variance of the change in each subtype group. These
 694 conservative calculations are based on comparing differences in rates of change for COPD-
 695 related phenotypes among two hypothetical groups of subjects ranging in size from 250 to 2000,

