11. Chest CT Scans will be performed to assess emphysema and airway disease in all subjects. An inspiratory chest CT scan will be performed with a radiation dose of 200 mAs in order to provide thorough assessment of small airway wall thickness and emphysema. An expiratory CT acquisition will be performed using a fixed x-ray tube current of 50 mAs to assess for air trapping. As of June 2015, in 3753 subjects scanned for COPDGene Phase 2 using a 200 mAs inspiratory scan and a 50 mAs expiratory scan, the estimated median total effective dose was 8.2 mSv. An additional inspiratory chest CT scan will be performed using a low dose protocol aligned with current clinical practice that utilizes dose modulation. Dose modulation automatically adjusts x-ray exposure for each patient to achieve a consistent level of image quality. The reference mAs for this scan will be set such that an average sized subject (~75 kg) with a normal build would receive an x-ray exposure (CTDIvol) of 3.0 mGy (corresponding roughly to an effective dose of 1.5mSv). The scans will be processed using filtered back projection and iterative reconstruction where feasible. X-ray exposure will automatically be adjusted higher or lower for larger or smaller subjects. The maximum exposure for the dose modulation acquisition will be set at 3.0 mSv. Comparison (quantitatively and qualitatively) of the two inspiratory CT scans will be performed to allow generalization of the study results to the low dose scans being performed clinically nationwide and enable application to clinical practice. Pending IRB approval, all Clinical Centers will perform this additional low dose inspiratory scan (absent local technical or logistical issues).

If the chest CT scans are done on the same day as the post-bronchodilator spirometry, the scan should be scheduled as soon as possible after albuterol. The time and date of the last bronchodilator prior to the CT scan will be captured. CT scans will be electronically transmitted to the Imaging Core at National Jewish Health by secure FTP site.

12. A urine pregnancy test will be performed on all premenopausal women prior to the chest CT scan to confirm that they are not pregnant.
13. Medical Record Review: medical records may be reviewed when available and with a signed release of records form documenting the subject's permission to obtain information about lung diseases, cancer, other medical conditions, and to determine cause of death, in the event of death.

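### Ten-year change in the inspiratory CT outcomes mixes disease change with a change of scan protocol, and the plan does not say which Phase 2 scan is the 5-year value

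*Protocol*

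**What the plan says.** **Phase 3** (Section V, item 12): "An inspiratory chest CT scan will be performed using a reduced dose protocol that utilizes" dose modulation. The reference setting gives an average-sized subject of about 75 kg an "exposure (CTDIvol) of 3.0 mGy (corresponding roughly to an effective dose of 1.5mSv"), with more for larger and less for smaller subjects and a maximum of 3.0 mSv. Scans are processed with filtered back projection and, where feasible, also with iterative reconstruction. No other inspiratory scan is described. The expiratory scan uses a fixed 50 mAs.

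**Phase 1** (Appendix A, Section III, item 10): one inspiratory scan at 200 mAs.

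**Phase 2** (Appendix B, Section III, item 11, repeated for the new non-smokers): "An inspiratory chest CT scan will be performed with a radiation dose of 200 mAs", and then "An additional inspiratory chest CT scan will be performed using a low dose protocol aligned with current clinical practice that utilizes dose modulation". The reference exposure and the 3.0 mSv maximum of this second scan are those of Phase 3. It depended on IRB approval and on the absence of local technical or logistical problems. The two inspiratory scans are to be compared so that results can be generalised to clinical low-dose scanning.

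**Analysis** (Section VII): the primary outcomes are change in FEV1, in adjusted lung density (PERC15 adjusted for lung volume) and in PRM functional small airway disease, and all-cause mortality. Longitudinal "analyses will be performed with quantitative imaging phenotypes from the Phase 1, 2, and 3" visits. Change in adjusted lung density between the 5- and 10-year visits is also a primary phenotype for the genetic and omics work.

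**The concern.** Adjusted lung density is built from a low percentile of the inspiratory density histogram. Image noise and reconstruction can move that percentile without any change in the lung. All subjects with Phase 1 and Phase 3 scans pass from 200 mAs to the reduced-dose scan, so ten-year change and the scan change coincide. PRM is affected so far as it uses the inspiratory scan; the Protocol does not describe how it is built.

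Section VII is otherwise specific. It sets out the volume adjustment, Box-Cox transformation, predictors, time-dependent covariates and a joint model with death. None of these handles acquisition.

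For the 5-to-10-year change, two Phase 2 inspiratory scans could each serve as the starting value. One matches Phase 3 and one does not, and the Protocol does not choose. A primary variable is therefore not fully defined, and the choice could be made after the results are seen.

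**Working it through.** **1. Which changes cross the scan switch**

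| Change | Start | End | Like scans? |
|---|---|---|---|
| Phase 1 to 2 | 200 mAs | 200 mAs (main scan) | yes, on the main scan |
| Phase 1 to 3 | 200 mAs | reduced dose | never |
| Phase 2 to 3, main scan | 200 mAs | reduced dose | no |
| Phase 2 to 3, additional scan | low dose | reduced dose | yes, where that scan exists |

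If only the 200 mAs scans are used for Phases 1 and 2, an acquisition term equals the Phase 3 visit indicator. It can then be separated from time only by assuming a shape for the time trend, such as a straight line. The paired Phase 2 scans remove that need.

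**2. Reproducing Table 2**

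The Protocol prints no SDs. Take two-sided alpha 0.05 (sidedness is not stated for these comparisons), equal groups and a normal approximation:

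SD = difference / [(1.96 + z_power) × √(2/n)]

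For adjusted lung density, difference 2, 46% power at n = 250:

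SD = 2 / [(1.960 − 0.100) × 0.0894] = 12.0

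This SD returns 46.0, 74.9, 96.1 and 100% at n = 250, 500, 1,000 and 2,000 (printed 46, 75, 96, 100). For a difference of 4 it returns 96.1% at n = 250 (printed 96). Solved in the same way, the other SDs are 291 ml for FEV1, 17.0 for PERC15 and 9.0 for % gas trapping. All 32 cells agree to the nearest percent; four were used to solve for the SDs and 28 are checks. The table is internally consistent and makes no allowance for a measurement shift between phases.

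**3. Mean change in the cohort**

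SE = 12.0/√4,500 = 0.18. A common shift passes entirely into the estimate. An assumed shift of 0.5, 1 or 2 units is 2.8, 5.6 or 11.2 SE.

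**4. Comparison of two subtypes**

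If the shift differs between groups by b and there is no true difference, the rejection rate is

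Φ(b/SE − 1.96) + Φ(−b/SE − 1.96), with SE = 12.0 × √(2/n).

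| Assumed b | n = 250 | 500 | 1,000 | 2,000 |
|---|---|---|---|---|
| 0 (common shift) | 5.0% | 5.0% | 5.0% | 5.0% |
| 0.5 | 7.5% | 10.1% | 15.3% | 26.0% |
| 1 | 15.3% | 26.0% | 46.0% | 74.9% |
| 2 | 46.0% | 74.9% | 96.1% | 100% |

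The bias can also hide a real effect. With a true difference of 2 and a differential shift of −0.5, power is 28.6, 50.5, 79.7 and 97.6% in place of 46, 75, 96 and 100%.

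The Protocol gives no size for the shift, so the values of b are assumptions.

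**5. Why a differential shift is plausible**

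Phase 3 exposure is adjusted to body size within a maximum, so the step from the 200 mAs scan need not be the same for everyone. Body size need not be balanced either: BMI above 35 excludes the non-smoker controls of Phases 2 and 3, and no such limit is listed for the smokers. How far body size differs between COPD subtypes is not documented.

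**The case against.** The strongest reply is that scan choice, acquisition covariates and calibration are usually left to a SAP or an imaging manual, and that naming three phases of imaging does not commit anyone to uncorrected pooling. A SAP not shown here may indeed settle this. But the Protocol itself defines the primary change variables and leaves one with two non-equivalent starting scans, so it should at least make that choice.

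Four stronger readings are tempting and are not supported:

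- **That every change ending at Phase 3 is contaminated.** Where the additional Phase 2 scan exists, the 5-to-10-year change can be taken between scans of the same type. Nor does the generalisation purpose given in Appendix B rule out using the pairs for calibration.
- **That the shift cannot cancel between subtypes.** A common shift does cancel, and no subtype is defined by body size.
- **That the size in Hounsfield units is known.** If dose is proportional to mAs, the 8.2 mSv median for the 200 + 50 mAs pair gives 8.2 × 200/250 = 6.56 mSv for the inspiratory part. That is 4.4 times 1.5 mSv, or about 2.1 times the noise (√4.37). Assuming noise of 10–20 HU and a parenchymal SD of 40–80 HU, PERC15 would fall by about 2–14 HU, but by only 0.8–5.2 HU at the 3.0 mSv maximum. The noise and SD values are not in the Protocol, a cohort median is set against an average-build subject, and the result is not on the volume-adjusted scale. These figures are not evidence of size.
- **That about 2,000 pairs exist.** 5,835 − 3,753 = 2,082 return visits fall outside the June 2015 count, but the Protocol does not say that the 3,753 lacked the additional scan. The number of pairs is unknown.

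Iterative reconstruction is also less of a threat than it may seem, because filtered back projection is already specified for the low-dose scans.

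**Conclusion.** The point holds in a limited form. Every Phase 1-to-3 change in an inspiratory CT outcome, and any Phase 2-to-3 change that starts from the 200 mAs scan, mixes disease change with the scan change. Mean change is biased by any common shift; with 4,500 returnees even 0.5 unit of adjusted density is 2.8 SE. Subtype comparisons keep their 5% error rate unless the shift differs by group. If it differs by 0.5 unit, type I error is 7.5–26%; if by 1 unit, 15–75%, at 250–2,000 per group.

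These figures rest on the SD of 12.0 recovered from Table 2, a two-sided 5% test and assumed shifts. FEV1, mortality and outcomes read from the expiratory scan alone are not affected. The one-year Phase 3a-to-3b change is not affected if both visits use the same scan protocol; none separate is described for 3b.

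**What to change.** Before Phase 3 CT change is analysed, state in Section VII or the SAP:

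1. The Phase 2 additional low-dose scan is the 5-year value for Phase 2-to-3 CT change wherever it exists. Report the number of subjects who have both Phase 2 inspiratory scans.
2. For Phase 1, and for Phase 2 subjects without that scan, 200 mAs values are converted with a calibration fitted on the paired Phase 2 scans, by lung density, body size and scanner. Its uncertainty is carried into the change estimates. An acquisition term alone will not do, because without the pairs it is not separable from visit.
3. Low-dose scans are quantified on their filtered back projection reconstructions, and the same reconstruction is used for the 200 mAs scans. The Protocol does not state how the latter were reconstructed, so this must be confirmed.
4. A sensitivity analysis uses like scans only.

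The cost is extra analysis on data already held, a like-for-like subset whose size the Protocol does not give, and slightly wider intervals. This concerns only which scans enter the analysis; no change to scan dose is proposed.

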355 and perform the walk test and sit to stand test. Approval to defer or continue will be
356 documented on the Safety Assessment form.

357 6. Pre- and post-bronchodilator spirometry will be performed on all subjects. The maneuvers
358 are performed according to American Thoracic Society standards. To obtain 3 acceptable
359 measures, the technician may ask the subject to perform up to 8 attempts. Spirometry is
360 performed before and then repeated approximately twenty minutes following the
361 administration of two puffs (180 mcg) of albuterol from a metered dose inhaler with a
362 spacer. Spirometry will ideally be performed with the subject in a seated position with a
363 nose clip in place. These results will be provided to the subject, subjects will be asked to
364 consent if they would like a copy of their test result sent to their primary care provider.

365 7. Diffusing capacity will be measured on all subjects after post-bronchodilator spirometry.
366 The test will be performed according to American Thoracic Society/European Respiratory
367 Society standards (8). In subjects using supplemental oxygen, oxygen will be removed, and
368 subjects will breathe room air for 10 minutes prior to the test. If resting saturation falls
369 below 82% or the subject becomes dyspneic prior to 10 minutes without oxygen, oxygen

370 therapy will be restarted as a safety precaution and the test will be performed without the
371 ten-minute oxygen washout. To obtain 2 reproducible measures, the test may be repeated
372 up to 5 times.

373 8. Standardized questionnaires will be completed by all subjects to assess respiratory
374 symptoms, smoking history, and other medical history. These questionnaires include the
375 St. George's Respiratory Questionnaire to assess health-related quality of life, the Medical
376 Outcomes SF-36 to assess generic quality of life, a COPD screening questionnaire
377 (CAPTURE) (32), the COPD Assessment Test (CAT) to assess COPD severity, and the
378 PROactive (33) and Duke Activity Status Index (DASI) (34) questionnaires to assess
379 physical activity. Questionnaires will be administered to obtain information about
380 respiratory history, medical history, anxiety and depression (Hospital Anxiety and
381 Depression Scale- HADS) (9). If data from the HADS are felt to be clinically significant,
382 they will be sent to the subject's primary care provider. Questions will be asked about

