 696 which will be created from the 4500 subjects with follow-up spirometry, clinical measures, and
 697 chest CT scans in Phase 3 (**Table 2**). Using these assumptions, there is adequate power to detect
 698 differences between subtype groups with as few as 250 subjects. By 2-sided log rank test, we
 699 will have virtually 100% power to detect a 15% difference in all-cause or cause-specific
 700 mortality between the slow and fast FEV₁ decline groups in Table 2.
 701

Table 2: Power (%) for Longitudinal Epidemiology Analysis

Outcome	Difference Between Groups over 10 yrs	Sample Size of Each Subtype Group for Pairwise Comparisons			
		250	500	1000	2000
FEV ₁ , ml	100	97	100	100	100
	200	100	100	100	100
PERC15	4	75	96	100	100
	8	100	100	100	100
Adjusted Lung Density	2	46	75	96	100
	4	96	100	100	100
% Gas trapping	2	70	94	100	100
	3	96	100	100	100

702
 703 The primary phenotypes for genetic, transcriptomic, and proteomic analysis will be each COPD
 704 subtype vs. smoking controls; the quantitative emphysema and airway disease axes; and the
 705 change in FEV₁ and adjusted lung density between the 5-year and 10-year visits. In addition, a
 706 number of secondary analyses will be performed, including: a) presence/absence of COPD
 707 (comparing subjects with GOLD 2-4 COPD to smoking controls); b) cross-sectional measures of
 708 CT emphysema, CT gas trapping, CT airway wall area, FEV₁, 6MWD, oxygen saturation,
 709 emphysema distribution, and chronic bronchitis; and c) longitudinal measures of exacerbation
 710 frequency and change in CT gas trapping, CT airway wall area, and 6MWD. Cross-sectional and
 711 longitudinal COPD-related phenotypes will be assessed within each COPD subtype and within
 712 the entire study population. Longitudinal imaging and lung function phenotypes will be assessed
 713 as both change over time (between the 5 and 10-year visits and across all three visits) and
 714 average outcomes over all three visits.
 715

716 Phase 2 blood RNA-Seq will be used to generate gene, exon, and isoform-level estimates of
 717 relative expression abundance. RNA-Seq data will be processed by the CDNM bioinformatics
 718 pipeline that addresses sequencing errors and other technical artifacts. Alignment to the human

719 reference genome will be performed with STAR(13), followed by multiple quantification and
720 analysis options, including DESeq2(14), DEXSeq(15), and voom/limma(16). While isoform-

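### Progression models adjust for unlagged change in pulmonary medications: if prescribing follows decline, predictor effects are attenuated and the medication coefficients are biased towards harm

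*Protocol*

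**What the plan says.** Protocol Section VII (Biostatistical Analysis) sets out the longitudinal epidemiology models. The primary outcomes are change in FEV1, adjusted lung density and functional small airway disease, together with all-cause mortality.

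Two statements in that paragraph matter here.

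- On covariates: "Longitudinal analysis will be performed including time-dependent covariates". These are then specified as "change in current smoking status and change in pulmonary medications".
- On predictors: the list of key variables to be assessed for the same outcomes includes "airway measures, respiratory symptoms (e.g., chronic bronchitis, dyspnea), respiratory" and continues "medications, and co-morbid illnesses (including lung cancer and coronary artery disease".

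The paragraph gives no lag, no rule that the medication change must come before the decline, and no model without the term. Its one stated protection against bias is joint modelling of progression and death, which deals with differential survival.

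The covariate lists for the Short-Term Follow-Up model and the proteomic model, also in Section VII, do not include medications.

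**The concern.** Section X describes the study as observational, without a therapeutic intervention, so respiratory treatment is whatever each subject's physician prescribes. If physicians add or intensify treatment because a patient is declining, a change in medication between two visits is partly caused by the decline between those visits.

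Entering that change as a covariate for the same interval conditions on a consequence of the outcome. Two things then follow.

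- Subtype and baseline-predictor effects on change in FEV1 or CT measures are attenuated, because part of the decline is credited to the medication term.
- The medication term takes a negative coefficient even when the drug does nothing. Because medications are also listed as key predictors, that coefficient is likely to be reported, and a reader could take it as treatment accelerating decline.

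**Working it through.** **Step 1: reproduce Table 2 and recover the SD.** The inputs are a "significance level of 0.05 and equal variance of the change in each subtype group" (taken as two-sided) and the FEV1 cell for 100 ml and 250 per group, printed as 97%. The SD of change is not printed. Power is Φ(δ / [SD·√(2/n)] − 1.96), so

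SD = 100 / [(1.960 + 1.881) × √(2/250)] = 100 / (3.841 × 0.0894) ≈ 291 ml.

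Check at n = 500: 100 / (291 × 0.0632) − 1.96 = 3.47, or 99.97%, printed as 100. Treating the other rows the same way gives SDs of 17.0 (PERC15), 12.0 (adjusted lung density) and 9.0 (gas trapping), and the remaining cells then reproduce to the printed rounding. This shows internal consistency; it does not verify the SDs independently.

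**Step 2: change-score model with an inert drug.** There are two equal groups with a true difference of 100 ml, SD 291 ml and no drug effect. Assumptions not taken from the documents: 30–50% of subjects escalate, and the odds of escalation rise by a fixed factor per SD of the subject's own decline. Change is regressed on group and escalation.

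| Assumed odds of escalation per SD of decline | Adjusted group difference (ml) | Coefficient of inert drug (ml) |
|---|---|---|
| 1 (no link) | 100 | 0 |
| 1.5 | 96–97 | about −114 |
| 2 | 90–92 | about −183 |
| 3 | 81–83 | about −260 |

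The attenuation equals the drug coefficient times the between-group difference in escalation. At odds of 2 with 30% escalating overall, 27.7% of the slower group and 32.3% of the faster group escalate, so the adjusted difference is 100 − 184 × (0.323 − 0.277) = 100 − 8.5 ≈ 91.5 ml.

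**Step 3: effect on power.** At log-odds of 0.5, 1 and 2 per SD (odds of about 1.65, 2.7 and 7.4), FEV1 power at 250 per group goes from 97% to 96%, 94% and 87%. For adjusted lung density (difference 2, 500 per group) it goes from 75% to 71%, 67% and 56%.

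**Step 4: three-visit mixed model.** With visits at 0, 5 and 10 years and the same three log-odds, the 10-year difference is about 98, 90 and 76 ml, against 95, 83 and 64 ml in the change-score model. The inert drug's coefficient is −97, −170 and −251 ml, significant in every replicate. With medication lagged by one visit, the adjusted and unadjusted differences agree (both about 98 ml) and false harm falls to 2–3%, its nominal rate.

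**Step 5: drugs that work.** Across odds of 1.5 to 3, a drug that truly raises FEV1 by 50 ml gets a coefficient of about −64 to −212 ml, and one that raises it by 100 ml gets about −13 to −162 ml. In these runs the adjusted difference is at or below the unadjusted one. The pattern is not universal: at log-odds of 0.25 (odds about 1.28), the 100 ml drug gets about +28 ml and the adjusted difference is slightly larger than the unadjusted one (99.1 against 98.6 ml).

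**The case against.** **The link is assumed.** The documents do not quantify how far prescribing follows decline. The nearest support is the temporary exclusion in Section III for new or increased systemic steroids taken for a respiratory disorder. This stands: with a weak link the loss in the subtype difference is only about 2–5%, and with none there is no bias.

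**Timing could be fixed elsewhere.** The protocol does not use the word concurrent, and a statistical analysis plan, not seen here, might define a lag. This stands in part. As written, a time-dependent change in medication, with no lag, accompanies an outcome that is itself change between visits; the natural reading puts both in the same interval.

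**Omitting treatment also has a price.** If a drug works, a model without the term is not free of bias either: with a 100 ml drug effect the unadjusted difference was 90–97 ml for log-odds of 0.5 to 2. This stands, and is why the term should be kept as a sensitivity analysis.

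**A predictor is not a treatment effect.** Aim 1 is prognostic, and the protocol never says that medication coefficients will be read causally. That is correct; an explicit sentence would prevent the misreading.

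**Stronger readings that the protocol does not support.** A reader might infer that the study itself drives prescribing by returning results, since Section V, item 6 says "These results will be provided to the subject, subjects will be asked to" agree to a copy going to their physician. That is a Phase 3 procedure, and Phase 3 is the last measurement in the three-visit change outcomes. The Phase 1 and Phase 2 spirometry and CT items in Appendices A and B state no such return. A reader might also infer that effects on mortality are pulled towards zero. Medication recorded at a visit precedes a later death, so the mechanism does not carry over, and no mortality calculation supports it.

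**Conclusion.** The point holds for the longitudinal epidemiology models of change in FEV1 and CT measures, conditionally on treatment being stepped up in response to decline. It does not extend to mortality, the Short-Term Follow-Up model or the proteomic model. No printed figure is wrong; Table 2 is an unadjusted pairwise calculation and reproduces.

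Attenuation of subtype and baseline-predictor effects is modest: roughly 3% to 19% of a 100 ml difference in the change-score model for odds of 1.5 to 3, and less in a three-visit mixed model. The medication coefficient is the more serious half. For an inert drug it exceeds in size the 100 ml difference being studied at every link from 1.5 upwards, and it can be negative for a drug that helps. These sizes rest on the back-solved SD of 291 ml, the assumed escalation rates and odds, and the same-interval reading. It would go too far to say that subtype effects must shrink or that medications must look harmful. The change is worth making because the covariate choice is explicit and the alternative costs little.

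**What to change.** In Section VII, for the primary progression models:

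1. Use medications recorded at the visit that opens each interval (Phase 1 for the first interval, Phase 2 for the second) as covariate and predictor.
2. Move concurrent change in pulmonary medications out of the primary adjustment set and into a labelled sensitivity analysis.
3. State that medication coefficients are prognostic associations and not treatment effects. This is still needed after the first change, because opening-visit medications also mark severity.

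The cost is analysis wording only: medications are recorded at the Phase 1, Phase 2 and Phase 3 visits (Appendix A, Section III, item 7; Appendix B, Section III, item 8; Section V, item 8). The small loss is that the primary model no longer removes a genuine effect of treatment begun within the interval; the sensitivity analysis shows the result with that term included.
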